**Table 4: Dose Adjustment Table**

Table 1. Dose Titration	
TSH <math>\mu</math>U/ml	Adjustment
Baseline <math>\pm</math> 0.5	No change
Baseline >0.5-7.0	Increase by 10%
>7.0	Increase by 20%
Baseline <0.5-0.1	Decrease by 10%
<0.1	Decrease by 20%

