5.1.1 Clinical indication for total thyroidectomy

5.1.2 Euthyroid (TSH at screening  $> 0.45 < 4.5$  mIU/mL)

5.1.3 Indication to total thyroidectomy for benign goiter or thyroid cancer not requiring suppressive thyroid hormone therapy

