## 8.3 Dosage and administration

### Study Dosing

Patients in the LT4 group will be started at a dose of 1.6 mcg/Kg (52), while patients assigned to LT4/LT3 group will have 25 mcg of LT4 substituted with 5 mcg LT3 twice daily, to mimic the average daily T3 production form the thyroid (36). For patients taking oral Semaglutide the initial levothyroxine dose will be reduced to 1.2 mcg/Kg (-25 mcg in case of randomization to the levothyroxine/liothyronine group) to correct for increase in absorption. The VCU Investigational Pharmacy will over-encapsulate LT4 plus placebo, or LT4 plus 5 mcg LT3 in “AM” and “PM” color coded capsules. Patients will be instructed to take the AM drug first thing in the morning with water only, and to wait at least 30 minutes before taking other medications coffee or breakfast. The PM dose will be taken at least 30 minutes before dinner. Dose adjustments will be performed at the 6-week and 3-month follow up visits by an unblinded endocrinologist ([name]) aiming to achieve and maintain a target TSH within the normal range and within  $\pm 0.5$  mIU/ml from the baseline (pre-surgery) TSH, according to the scheme in Table 1. Doses will be rounded to the nearest available formulation. No changes will be made in LT3.

Patients and their healthcare providers will be encouraged to inform the study team of any change in medications. An information card containing a basic description of the protocol, study medications, and contact information of the PI and study coordinator will be given to the study. **participants with instructions to show it at any encounter with healthcare providers for the duration of the study.**

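### Table 4 gives two dose instructions for a TSH under 0.1 when baseline TSH is below 0.6, and its no-change row omits the normal-range half of the section 8.3 target

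*Combined protocol and SAP*

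**What the plan says.** Section 8.3 (Study Dosing) gives dose adjustment at the 6-week and 3-month visits to an unblinded endocrinologist, "aiming to achieve and maintain a target TSH within the normal range and within" 0.5 "from the baseline (pre-surgery) TSH, according to the scheme in Table 1". The target therefore has two parts that must hold together. The scheme meant is the dose titration table, which is numbered Table 4 in the protocol and carries an inner caption calling it Table 1.

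Table 4 has five rows:
- baseline ± 0.5: dose unchanged;
- above that band, up to 7.0: "Increase by 10" per cent;
- above 7.0: increase by 20 per cent;
- "Baseline <0.5-0.1": decrease by 10 per cent;
- below 0.1: "Decrease by 20" per cent.

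The first row is relative to the patient's own baseline. The last is an absolute cut-off. The table does not mention the normal range and does not say which row prevails if two apply.

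Section 8.3 gives no figures for the normal range. The only numeric euthyroid range set for this trial is inclusion criterion 5.1.2, "Euthyroid (TSH at screening" above 0.45 and below 4.5). The Schedule of Events shows TSH drawn again at the baseline visit, so the value that anchors titration is a different sample from the one that decides eligibility.

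**The concern.** A titration table should return one action for each combination of baseline and follow-up TSH, and that action should serve the target in the text. Table 4 seems to fail on both counts for patients whose baseline is close to a limit.

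Where two rows apply, the action is left to the judgement of a physician who knows the arm. Where the table says to leave the dose alone although TSH is outside the normal range, following the table exactly leaves the patient off the protocol's own target. There are only two scheduled adjustments. A value left off target at 3 months has no further scheduled adjustment before the 6-month assessment. The stakes are consistent titration and patient safety in a small set of cases, in a trial of 15 patients per arm.

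**Working it through.** **Inputs.** From Table 4: the half-width 0.5 and the cut-offs 0.1 and 7.0. From section 8.3: the joint target and the pre-surgery anchor. From criterion 5.1.2: 0.45 and 4.5, used as an assumption in the third step. The printed units differ between the text and the table; I take all TSH figures to be on one scale. Write B for baseline TSH. The plan states no figure of its own to reproduce here.

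**1. Overlap between rows.** The no-change band runs from B − 0.5 to B + 0.5. It meets the row for TSH below 0.1 when B − 0.5 < 0.1, that is, when B < 0.6.
- B = 0.50: the band is 0 to 1.00, so every TSH below 0.1 matches both rows. Follow-up 0.05 differs from baseline by 0.45, so the dose is unchanged by the first row; it is also below 0.1, so the dose falls by 20 per cent by the last row.
- B = 0.55: the band starts at 0.05, so TSH from 0.05 to just under 0.1 matches both.
- B = 0.60: the band starts at 0.10 and the overlap is gone.

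The 10 per cent decrease row, read as 0.1 up to just below B − 0.5, is empty for B ≤ 0.6, so these patients have no intermediate step.

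**2. The rest of the table.** I stepped through B from 0.46 to 4.49 by 0.01 and TSH from 0.005 to 10 by 0.005. Double matches occurred only for B from 0.46 to 0.59, and only between these two rows. No TSH value was left without a row. The upper rows cannot collide, because the largest B + 0.5 is 4.99, below 7.0.

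Reading the second and fourth rows as absolute cut-offs does not help. Baseline 0.50 with TSH 0.05 still matches two rows, and new overlaps appear: baseline 2.0 with TSH 2.0 matches both the no-change and the 10 per cent increase rows.

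**3. No-change band against the normal range.** For a range from L to U, part of the band is outside when B < L + 0.5 or B > U − 0.5. With L = 0.45 and U = 4.5 the cut-points are 0.45 + 0.5 = 0.95 and 4.5 − 0.5 = 4.0.

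| Baseline | No-change band | Width outside 0.45–4.5 | Share of band |
|---|---|---|---|
| 0.50 | 0–1.00 | 0.45 | 45% |
| 0.70 | 0.20–1.20 | 0.25 | 25% |
| 0.95 | 0.45–1.45 | 0 | 0% |
| 4.00 | 3.50–4.50 | 0 | 0% |
| 4.20 | 3.70–4.70 | 0.20 | 20% |

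For example, baseline 0.70 with TSH 0.25, or baseline 4.20 with TSH 4.65, is left unchanged by the table but is off target by the text under this assumption. A different normal range moves 0.95 and 4.0, but any baseline within 0.5 of a limit is still affected.

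**The case against.** The strongest reply is that text and table can be read together: section 8.3 states the aim, the table serves it, and the normal-range condition silently limits the no-change row. That is a sensible reading, but the protocol does not state it, and it leaves a hole. With baseline 0.70 and TSH 0.25, the 10 per cent decrease row covers only 0.1 to just under 0.20. With baseline 4.20 and TSH 4.65, the 10 per cent increase row starts above 4.70. If the no-change row is withdrawn, neither value has a row. The reading also does not settle which row applies below 0.1 when baseline is under 0.6.

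Two further objections stand as limits. The double instruction needs both a baseline below 0.6 and a follow-up below 0.1, among 30 patients with two adjustment points. Other protections also exist: an endocrinologist makes the adjustments, section 6.2 lets the study physician take a patient off treatment for safety, and section 12 provides an independent monitoring board. None of these resolves the table, but they make it wrong to assume that a suppressed TSH would simply be ignored.

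A reader might infer that the flaw breaks the comparison of the arms at matched TSH. The documents do not support that. Every value in the no-change row is within 0.5 of that patient's own pre-surgery TSH, which is what section 2.2 sets out to restore, and the same table applies in both arms. Knowledge of the arm could matter where the action is discretionary, but nothing shows an imbalance.

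**Conclusion.** Table 4 is internally inconsistent and does not match section 8.3. The row overlap for baselines below 0.6 follows from the table's own figures. The missing normal-range condition is also plain from the text; only the cut-points 0.95 and 4.0 depend on taking 0.45–4.5 as the normal range.

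Three limits on size apply:
- For a baseline inside 0.45–4.5 the no-change band lies partly, never wholly, outside that range, because it is centred on a value within it.
- The limits 0.45 and 4.5 bind TSH at screening. Baseline TSH could differ, and could even be below 0.45, so they are not strict bounds on baseline.
- A reader might turn the affected intervals into percentages of patients. No TSH distribution is given, so frequency is unknown.

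This is a contradictory rule worth correcting for safety and consistent titration. It is not evidence of bias in the weight or energy-expenditure results.

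**What to change.** Reconcile Table 4 with section 8.3 so that, for every possible baseline, each follow-up TSH falls in exactly one row and the action in that row agrees with the joint target. State the numeric normal range that section 8.3 relies on. Say which rule prevails where the baseline-relative and absolute criteria meet. The investigators decide the precedence and the actions; none is proposed here. The cost is a clarification to one table and its covering paragraph, with no new visits, samples or tests.

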## **9 STUDY PROCEDURES**

### **STUDY VISIT PROCEDURES**

The entire protocol consists of five visits: one screening visit, one baseline visit, one dose adjustment visit, and three inpatient overnight admissions (referred as “phenotyping visits”). The follow up study visits will occur in a +/- 7-day window. Study participants will be admitted for their baseline phenotyping visit before surgery. Randomization will be performed at the time of the baseline visit. On discharge from the hospital, (postoperative day 1 or 2) patients will start the study drugs. An outpatient visit for dose adjustment will occur six weeks following surgery. Three months after surgery, patients will have a second overnight phenotyping visit and therapy adjustment. A third phenotyping visit (end of study) will be performed six months after surgery. The overnight phenotyping visits will be identical, except no DXA scan will be performed at baseline and during the 6-month post-op visit.

The summary of the procedures is presented in the table 2 (study scheme)

## **9.1 Informed Consent**

Prior to performing any study-related procedures, the patient must sign and date an Institutional Review Board (IRB)-approved informed consent form (ICF). The informed consent process must be thoroughly documented in the patient's record.

## **9.2 Medical History:**

The following information will be gathered from the patient and from the review of the medical records:

- Age
- Self-reported race/ethnicity
- Medical History
- Prior history of cardiovascular disease, diabetes, hypertension, dyslipidemia.
- Prior surgical history
- Social history (use of tobacco or alcohol)
- History of Medication usage
- Female subjects will be asked to provide a menstrual history,
  - use of contraception, and
  - self-reported pregnancy status planning for the study period.

## **9.3 Physical Examination**

An abbreviated physical examination will be performed, and the following organ systems will be evaluated:

- Vital signs: oral temperature and blood pressure
- Neurological exam: focal deficit, resting tremor, reflexes
- Lungs: sounds
- Cardiovascular: rate, rhythm, murmur, peripheral pulses
- Abdomen: tenderness, organomegaly

## **9.4 Energy Expenditure Recordings**

Each of the three phenotyping visits will include an up to 24-hour recording of energy expenditure in the whole room calorimeter. The room calorimeter is a 10' x 10' x7'6" room with a window and transparent plexiglass wall. The room is fitted with TV, phone, hospital bed, small desk, a toilet behind a privacy screen and a vanity. Meals are passed through an air lock port. The room is fitted with Wi-Fi and the door has no lock. The enclosed space may cause some minimal discomfort and the ventilation can be noisy, non-dissimilar to a commercial airplane. Study volunteers will be instructed they can step out the room and withdraw from the study at any time, and there is no lock in the calorimeter's door. Volunteers will enter the WRIC at the earliest at11:00 and will receive standardized meals at 13:00 (if already entered in the WRIC), and at 18:00, each representing 1/3 of the estimated EE with the following macronutrient composition: 50% carbohydrate, 20% protein, 30% fat.

Approximate total energy needs for weight maintenance will be calculated using the Mifflin-St. Jeor equation (89). EE recording will be completed at approximately 11:00 of the following day.

## **9.5 Anthropometric data**

Height and weight will be recorded using a calibrated stadiometer. Temperature, heart rate, and blood pressure will be recorded by a research nurse.

## **9.6 Blood Collection**

### **Venous Blood Sample Collection**

We will insert a needle in a vein to collect blood samples at specified times. Study subjects will undergo one venipuncture during each of the study visits. Altogether, five blood samples will be collected throughout the study for a total of approximately one and a half cup of blood. All the samples collected will be for the research study, except for the measurement of TSH that will be used to adjust the therapy. We will store and analyze your samples for lipids (cholesterol, HDL, triglycerides), Thyroid stimulating Hormone TSH (determinations for dose adjustments), Free T4 and total T3. TPO antibodies and HbA1c or fructosamine < 325 mcmol/l in substitution of HbA1c to reflect recent improvement in diabetes control (the latter for patients with diabetes) will be collected at the screening visit to help determine the presence of autoimmune thyroid disease and, limited to patients with diabetes, the control of the disease. Blood samples will be collected at screening, baseline (pre-surgery), 3-month and 6-month study visits.

We will collect two 5 mL of blood will be collected in a Na-EDTA tube (purple top) at the baseline visit to obtain HbA1c and to extract genomic DNA. Approximately 20 mL of blood will be collected in SST tubes with (no additives except serum separator) each session for TSH, thyroid hormones (total T3 and free T4), serum lipids and storage. No more than 320 mL of blood will be collected over the course of the five sessions. Serum will be separated by centrifugation, aliquoted in 1 mL cryovials and stored in -80°C freezers in the Department of Endocrine laboratory in Sanger Hall. Samples will be stored as described above for future analyses for studies. The Thr92Ala D2 polymorphism will be analyzed in the Department of Endocrine laboratory. [name] will supervise the performance of these analyses.

## **9.7 Accelerometers**

The accelerometers are sensing devices that measure a moving object's acceleration and can detect frequency and intensity of human movement. They are very similar to "Fitbit" or other exercise recording devices. Maybe done depending upon availability

## **9.8 Genetic Material**

Genetic material will be collected during the study to study whether common gene variations called "Single Nucleotide Polymorphisms" (SNPs) in gene that regulate the thyroid hormone

signaling affect the response to the therapy. We do not plan to screen for genetic disease, and the information collected are without clinical interest, thus the information will not be provided to the volunteers. No genome wide association study will be performed, and the genetic material will be disposed of at the end of the study. Study volunteers can opt out the collection of genetic material.

### **9.9 Quality of Life assessment**

Study participants will be administered ThyPRO-39, a thyroid specific quality of life instrument at the baseline (pre-surgery), 3-month and 6-month visit. This questionnaire helps the researchers to measure the intensity of the symptoms associated with hypothyroidism, and their changes in relation to the therapy. Some individual may experience discomfort by gaining introspection in their condition.

### **9.10 DXA Scan (Dual-energy x-ray Absorptiometry):**

**DXA** stands for dual-energy x-ray absorptiometry (also known as a **DEXA scan**). A simple, 10-minute test takes a comprehensive snapshot of your exact breakdown of bone, fat tissue, and muscle mass. The DXA scan is the most accurate and precise body fat test available. There are not any special preparations needed, except to stop taking any calcium supplements for 24 hours before the test. Study participants are requested to lay still on a table while a sensor (similar to an X-ray machine) moves over the body from the head to the feet. Wear comfortable clothing. Study volunteers will undergo (DXA scan) at the baseline and six-month visits. The only potential risk associated with DXA scan is the exposure to radioactivity.

### **9.11 Echocardiogram (echo)**

An echocardiogram will be performed at the baseline, three and six-month visits to assess the myocardial structure and ejection fraction.

## **10 STUDY VISITS**

### **10.1 Overall study schedule**

Study schedule summarized (Table 1)

### **10.2 Screening/Inclusion**

#### **(Screening Visit)**

Trained Endocrinologists and study staff will conduct the screening Visit

## Study Identifiers

At screening, each volunteer will be assigned a sequential volunteer ID number (EMT-01M25, EMT-02F27, etc) that will indicate study identifier, sequential number of screening, sex, age). The suffix "E" will be applied to volunteer who met the inclusion criteria and were enrolled in the study. The volunteer ID number will be used for all study related procedures. The key to the volunteer ID number will be maintained by the study coordinator and will be kept in a secure location behind a locked door ([name]). Only allowed investigators on the study roster will have access to the key (upon request). The key will be destroyed at the end of study following VCU policy.

## Screening Visit will include:

- Informed Consent (section 9 (9.1))
- Anthropometric information, which include measures of height, weight, temperature, and body composition and blood pressure.(section 9 (9.5))
- A physical exam will be performed by the study physician (section 9 (9.3))
- The study team will collect the following information (section 9 (9.2))
  - demographics,
  - Medical history
  - Prior surgical history,
  - social history,
  - history of medication usage;
- Female subjects will be asked to provide a menstrual history,
  - use of contraception, and
  - Self-reported pregnancy status for the study period.
- Blood sampling: (section 9(9.6))
  - Thyroid peroxidase antibody (TPO antibodies)
  - Thyroid Stimulating Hormone (TSH)
  - HgA1c (for subjects with a history of diabetes)
- Review the inclusion /exclusion to determine eligibility section (5 5.1 and 5.2)

The Endocrinologist will determine study eligibility. Eligible subjects will proceed to three identical overnight **Phenotyping Visits and one outpatient Dose Adjustment Visit:**

- (Visit 1) Baseline

- (Visit 2) Three month after surgery and
- 6 Week Dose Adjustment Visit
- (Visit 3) Six month Visit End of study

### **10.3 Phenotype Visit 1 (Baseline)**

Once the surgical thyroidectomy date has been determined, subjects will be scheduled for the Phenotype (Visit 1) Baseline Visit

#### **10.3.1 Two (2) days prior to the Phenotype Visit 1 Baseline**

Subjects will be instructed to:

- refrain from strenuous exercise
- Remain on a regular diet

#### **10.3.2 Prior to Surgery Phenotype Visit 1 Baseline**

Subjects will be admitted to the hospital on the Clinical Research Services Unit for an inpatient stay in the whole room indirect calorimeter (WRIC) prior to Thyroidectomy surgery (Standard of care)

- **Randomization** will be performed
- **The following will be performed in the am Prior to Entry into the WRIC**
  - An abbreviated history and physical examination.
  - Echocardiogram recorded,
  - Administration of ThyPRO-39.
  - Accelerometers Fitting - subject will be fitted with five (one on each limb plus chest) to record spontaneous movements. (maybe done depending upon availability)
  - DXA scan
  -
- **The subject will enter the WRIC at 11:00 am**
- **Dietary Meals**
  - The study will provide Standardized Meals.
  - Standardized Meals will be served at 13:00 (if already entered in the WRIC), and at 18:00, each representing 1/3 of the estimated EE with the following macronutrient composition: 50% carbohydrate, 20% protein, 30% fat. Approximate total energy needs for weight maintenance will be calculated using the Mifflin-St. Jeor equation (89). EE recording will be completed at approximately 11:00 of the following day,

- EE recording will be completed at approximately 11:00 of the following day,
- Blood sampling: TSH, Genomic DNA, Free T4, Free T3, Lipids, serum for storage
- Dispense Study Medication prior to discharge

On discharge from the hospital, (postoperative day 1 or 2) patients will start the study drugs

#### **10.4 Six Week Post Surgery**

An outpatient visit for dose adjustment will occur six weeks following surgery.

- An abbreviated history and physical examination.
- Blood sampling: TSH, serum for storage
- Dose Adjustment
- Dispense Study Medication prior to discharge

#### **10.5 Phenotype Visit 2 (Month 3)**

Three months after surgery, patients will have a second overnight phenotyping visit and Medication adjustment.

- **The following will be performed in the am Prior to Entry into the WRIC**
  - An abbreviated history and physical examination
  - Pill count
  - Echocardiogram recorded,
  - Administration of ThyPRO-39.
  - Accelerometers Fitting - subject will be fitted with five (one on each limb plus chest) to record spontaneous movements. (maybe done depending upon availability)
  -
- **The subject will enter the WRIC at 11:00 am**
- **Dietary Meals**
  - The study will provide Standardized Meals.
  - Standardized Meals will be served at 13:00 (if already entered in the WRIC), and at 18:00, each representing 1/3 of the estimated EE with the following macronutrient composition: 50% carbohydrate, 20% protein, 30% fat. Approximate total energy needs for weight maintenance will be calculated using the Mifflin-St. Jeor equation (89). EE recording will be completed at approximately 11:00 of the following day,

- EE recording will be completed at approximately 11:00 of the following day,
- Blood sampling: TSH, Free T4, Free T3, Lipids, serum for storage
- Dispense Study Medication prior to discharge

Note: No DXA scan will be performed during the 3-month post-op visit.

## **10.6 Phenotype Visit 3 (Month 6)**

Six months after surgery a third phenotyping visit (end of study).

- **The following will be performed in the am Prior to Entry into the WRIC**
  - An abbreviated history and physical examination
  - Pill count
  - Echocardiogram recorded
  - Administration of ThyPRO-39
  - Accelerometers Fitting - subject will be fitted with five (one on each limb plus chest) to record spontaneous movements. (maybe done depending upon availability)
  - DXA scan
  -
- **The subject will enter the WRIC at 11:00 am**
- **Dietary Meals**
  - The study will provide Standardized Meals.
  - Standardized Meals will be served at 13:00 (if already entered in the WRIC), and at 18:00, each representing 1/3 of the estimated EE with the following macronutrient composition: 50% carbohydrate, 20% protein, 30% fat. Approximate total energy needs for weight maintenance will be calculated using the Mifflin-St. Jeor equation (89). EE recording will be completed at approximately 11:00 of the following day,
  - EE recording will be completed at approximately 11:00 of the following day,
  - Blood sampling: TSH, Free T4, Free T3, Lipids, serum for storage
  - Collect Medication prior to discharge

